## **2. Projected Number of Clinics**

We anticipate that the 15 intervention clinics from the parent study will be included in this study and will be randomized to receive or not receive the suicide prevention module.

## **3. Statistical Power**

Based on preliminary data, 1619 diagnosed (median=89, range=39-267 per clinic) and 3349 at-risk (median=41, range=19-129) patients were seen in the clinics eligible for the parent study over the course of one year for a total of 4968 (median=130, range=66-387) OUD-CDS-eligible patients. Assuming that 5%, 10% or 20% of approximately 2500 patients are evaluated and considered at high risk for suicide, we estimate that 125 (2500 \* 5%), 250 or 500 patients will be eligible for this study over one year of accrual.

A power analysis estimated the minimum detectable risk ratio for CSSRS and visit rates in intervention relative to control clinics. It relied on data-informed assumptions regarding the number of randomized clinics (n=15) and eligible patients per clinic (pts/clin =8, 16, 33); a range of clinic intraclass correlations consistent with those observed for other process measures at HealthPartners (ICCclin = 0.01, 0.03, 0.05); and outcome likelihood estimates in control clinics (screening=1%, 3%, 5%; visit rate=2, 3, 4/year).

Assuming 3% of control clinic patients are screened for suicide risk, the analysis will be powered (power=0.80,  $\alpha$ 2=0.05) to detect an outcome should at least 14.2% (ICCclin=0.01, 33 pts/clin, risk ratio = 4.72) to 65.0% (ICCclin=0.05, 8 pts/clin, RR=21.66) of intervention clinic patients be screened. The comparable range of detectable differences for outcomes with a 5% screening rate among control clinic patients is 16.8% (RR=3.36) to 54.8% (RR=5.80).

Power for Aim 2 analyses is not as sensitive to sample size assumptions. Under the most generous assumptions (ICCclin= 0.01, 33 pts/clin), small increases in visits rates (2.4 vs. 2.0, RR=1.22; 4.6 vs. 4.0, RR=1.15) will be detectable. Larger but still attainable increases (3.0 vs. 2.0, RR=1.49; 5.3 vs. 4.0, RR=1.33) will be detectable under the most conservative of assumptions (ICCclin=0.05, 8 pts/clin).

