**E. Study Design**

**1. Overview of Study Design.** When a patient is at elevated risk of suicide, the PCC will be prompted by Opioid Wizard to complete the CSSRS, easily available to all PCCs in the EHR and saved as discrete data elements. Risk-based (depending on CSSRS score) referral and follow-up recommendations for suicide prevention will be given, with specific care recommendations ranging from care as usual (very low risk) to referral to behavioral health for evaluation and safety planning (moderate to high risk) to immediate evaluation in the emergency department and potential inpatient admission (very high risk), building on workflows developed for use by care managers in our recently completed suicide prevention trial of over 19,000 people at elevated risk of suicide.

The MHRN suicide risk models will be programmed into the EHR, a rigorous process that will take approximately 6 months. This process includes building the model in a testing environment in the EHR, testing the model with fictitious patients in a EHR testing environment and conducting chart audits, revising as needed, testing the model in a different EHR testing environment with real patient data, revising as needed, testing the model by running it silently in the EHR production environment and conducting chart audits, and revising as needed. This is followed by testing in the EHR production environment with 5-15 physicians in 1-2 pilot clinics. Prior to the go-live date for the suicide risk calculator, training on use and interpretation of the suicide risk model and the CSSRS will be provided to all PCCs and their rooming staff in intervention clinics. Training for control clinics will be separate and will provide training on the use of the CSSRS.

**2. Duration of Study and Visit Schedule.** In the parent trial, HealthPartners primary care clinics (n=30) will be randomized to receive or not receive access to the OUD-CDS. In this supplemental study, the clinics receiving access to the OUD-CDS (n=15) will be further randomized (1:1) to receive or not receive access to the MHRN suicide risk models and associated CDS. PCCs in HealthPartners clinics with CDS access will have access to the main OUD-CDS intervention for up to 30 months from date of implementation. PCCs in HealthPartners clinics randomized to the suicide model intervention will have access to the suicide supplement intervention for up to 12 months from date of implementation.

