**3. Patients:** To be eligible for inclusion in the parent study (and therefore also this supplemental study), a patient must: (a) be aged 18-75 years, inclusive; (b) have an OUD diagnosis, be prescribed an active MOUD, or be identified by the opioid risk models as being at high risk of OUD or overdose; and (c) be identified at high risk of suicide by the suicide risk models. There are no exclusions for pregnancy, lactation, or mental health or behavioral health diagnoses. The first visit at which all eligibility criteria are met will be the index visit. Patients who meet the following criteria at their index visit will be excluded and not be exposed to the intervention: (a) active parenteral chemotherapy within the last year; (b) stage 4 or equivalent cancer diagnoses; or (c) enrolled in hospice or palliative care programs. Patients will accrue in the first 9 months of the 12 month intervention period to allow for at least 3 months of data collection for every patient. All PCCs and eligible patients will be attributed to the clinic at which they practice (PCC) or their index visit took place (patients) and to the arm to which their clinic is randomly assigned.

**Consent:** We will request and anticipate receiving a waiver of written informed consent from the IRB for patient participation because the study is minimal or less than minimal risk

Table 1. Summary of Clinic Access & Training

| Suicide Supplement Intervention Clinics   | Suicide Supplement Control Clinics |
|---|------------------------------------|
| EHR alerts to patients at elevated risk of suicide per the MHRN suicide risk models                                   | No EHR alerts                      |
| EHR access to the CSSRS that includes risk-based referral and follow-up recommendations for care based on CSSRS score |                                    |
| Training on use of the CSSRS via live and recorded webinars and follow-up handouts                                    |                                    |

compared to the risk associated with any primary care encounter, and because the study could not practically be conducted if written informed consent were required to be obtained in the context of busy community-based primary care clinics. We have requested and received such waivers in several similar prior studies, including the parent study. Patients who have requested non-participation in research studies will be excluded from all analyses.

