### **4. Follow-Up**

There is no study-determined visit schedule. Patient visits with their PCCs in the randomized clinics will take place without any interference or involvement from the study team. Primary care visits that take place after the index visit and prior to the end of the observation period will be denoted as post-index visits. The OUD-CDS will flag the occurrence of all index and post-index visits so that EHR data documented from each may be extracted and assembled into an analytic dataset.

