### **I. Randomization**

In the parent trial, HealthPartners primary care clinics (n=30) will be randomized to receive or not receive the intervention. In this supplemental study, simple randomization will allocate the intervention clinics (n=15) approximately evenly to receive or not receive access to the MHRN suicide risk models and associated CDS.

Each patient will be considered to belong to the clinic in which his or her first visit that is eligible for the OUD-CDS intervention (i.e., index visit) takes place, and as such will be in the treatment group to which their clinic was randomly assigned. Post-index visits may take place in the same or different clinics or treatment groups relative to the index visit and may or may not be eligible for the OUD-CDS to offer treatment recommendations. In keeping with an intent-to-treat principle, all index and post-index visits and outcome measures for each patient will be attributed to the treatment group assignment of the clinic where the index visit took place.

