### **J. Analysis**

#### **1. Study Hypotheses**

**H1:** Opioid Wizard-eligible patients (patients with OUD or at elevated risk of OUD/overdose) with elevated suicide risk in intervention clinics will have higher rates of completed CSSRS assessments than similar patients in control clinics.

**H2:** Opioid Wizard-eligible patients with elevated suicide risk in intervention clinics will have higher rates of engagement in their outpatient mental health care than similar patients in control clinics.

The hypotheses for this supplemental study predict that the Opioid Wizard + Suicide Risk Prediction intervention will increase (a) the likelihood that Opioid Wizard-eligible patients with elevated suicide risk are assessed at the index visit for immediate suicide risk using the CSSRS (H1); and (b) the rate of post-index primary care visits with a mental health diagnosis or with a behavioral health clinician (H2). These hypotheses will be tested using generalized linear mixed models so that each outcome may be estimated among intervention relative to control clinics while accounting for patient outcomes clustered within randomized clinics via a random clinic intercept. Both outcomes will likely be normalized with a Poisson-Normal link function, although the distribution of visits may warrant using a Negative Binomial-Normal link.

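### J.3 sizes the study on one year of accrual, but F.3 allows nine months and so 3 to 12 months of follow-up; H2 power at the stated ratios falls below 0.80

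*Combined protocol and SAP*

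**What the plan says.** **Accrual in the power section.** J.3 starts from about 2500 patients eligible for the opioid decision support, based on preliminary counts over one year. It assumes 5%, 10% or 20% are at high suicide risk. The first gives 125; for the other two it says "250 or 500 patients will be eligible for this study over one year of accrual". Divided by 15 clinics these are its inputs of 8, 16 and 33 per clinic.

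**Accrual in the design.** F.3 says: "Patients will accrue in the first 9 months of the 12 month intervention period to allow for at least 3 months of data collection". It also defines entry: "The first visit at which all eligibility criteria are met will be the index visit". Section O does not mention nine months but fits it: 12 months of intervention and data collection, with at least 3 months of follow-up per patient. E.2 says that clinicians in the intervention clinics "will have access to the suicide supplement intervention for up to 12 months from date of implementation".

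**What H2 counts.** J.1 defines H2 as a rate of post-index visits. G.4 defines post-index visits as "Primary care visits that take place after the index visit and prior to the end of the observation period". H1, by contrast, is assessed at the index visit.

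**Stated detectable effects for H2.** With ICC 0.01 and 33 patients per clinic, J.3 gives rate ratios of 1.22 (control rate 2 per year) and 1.15 (4 per year). With ICC 0.05 and 8 per clinic, it gives 1.49 and 1.33. It states no follow-up length.

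**The concern.** The two accrual periods conflict, and the shorter one costs H2 information in two ways. Patients whose first qualifying visit falls in months 10 to 12 are not enrolled. Those who are enrolled are followed for 3 to 12 months, and their mean follow-up reaches one year only if every index visit falls on the go-live day.

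The number of clinics is fixed at 15 and all eligible patients are taken, so J.3 is the plan's only statement of what the study can detect. If its ratios assume more person-time than the design can collect, a null H2 result would be judged against power the study never had.

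**Working it through.** **Inputs.** From J.3: m = 33 with ICC 0.01, or m = 8 with ICC 0.05; control rate λ = 2 or 4 per year; power 0.80; two-sided α 0.05. From section I: "simple randomization will allocate the intervention clinics (n=15) approximately evenly", taken as 7 control and 8 intervention clinics. The reverse split moves power by about 0.01. T is mean follow-up in years.

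**Formulas.** The sponsor's method is not given, so two standard forms were used.

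- Design effect: SE² = [1 + (m−1)·ICC] × [1/(7mλT) + 1/(8mλ·RR·T)].
- Random intercept: SE² = [s² + 1/(mλT)]/7 + [s² + 1/(mλ·RR·T)]/8, with s² = ICC/((1−ICC)λ).

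The detectable ratio solves ln(RR) = (1.96 + 0.842)·SE. Power at a given ratio is Φ(ln(RR)/SE − 1.96).

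**Step 1: J.3's own figures.**

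| Basis | 33/clinic, rate 2 | 33/clinic, rate 4 | 8/clinic, rate 2 | 8/clinic, rate 4 |
|---|---|---|---|---|
| J.3 | 1.22 | 1.15 | 1.49 | 1.33 |
| Design effect, T = 1, full count | 1.217 | 1.151 | 1.474 | 1.324 |
| Random intercept, T = 1, full count | 1.221 | 1.153 | 1.503 | 1.340 |
| Design effect, T = 0.95, full count | 1.223 | 1.155 | 1.488 | 1.333 |
| Design effect, T = 0.625, full count | 1.279 | 1.193 | 1.621 | 1.419 |

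The stated ratios therefore correspond to the one-year count and about one person-year per patient. That person-year is an inference; J.3 does not state it.

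**Step 2: one case in full (33 per clinic, ICC 0.01, rate 2, RR 1.22; design effect).**

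- J.3 basis: the design effect is 1 + 32 × 0.01 = 1.32. SE = √[1.32 × (1/462 + 1/644.2)] = 0.0700. Then ln(1.22)/0.0700 = 0.1989/0.0700 = 2.84, and power is Φ(0.88) = 0.81.
- Even entry over nine months: the count is 9/12 = 0.75 of the one-year figure, so m = 24.75. Mean follow-up is (3 + 12)/2 = 7.5 months, so T = 0.625. The design effect is 1.2375 and SE = 0.0991. Then 0.1989/0.0991 = 2.01, and power is Φ(0.05) = 0.52.

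**Step 3: other entry patterns.** Even entry may be pessimistic, because patients already under regular care tend to have their first visit early. If first visits occur at r per year (exponential waiting time) and enrolment stops at month 9:

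- share of the one-year count = (1 − e^(−0.75r))/(1 − e^(−r))
- T = 1 − [1/r − 0.75·e^(−0.75r)/(1 − e^(−0.75r))]

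Power at J.3's four ratios (range over the four cases):

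| Entry pattern (assumed) | Share of count | T (years) | Design effect | Random intercept |
|---|---|---|---|---|
| All at go-live | 100% | 1 | 0.80-0.82 | 0.78-0.80 |
| 12 first visits per year | 100% | 0.917 | 0.76-0.79 | 0.75-0.77 |
| 8 per year | 99.8% | 0.877 | 0.74-0.77 | 0.74-0.76 |
| 6 per year | 99.1% | 0.842 | 0.72-0.75 | 0.73-0.74 |
| 4 per year | 96.8% | 0.789 | 0.69-0.72 | 0.70-0.71 |
| 2 per year | 89.8% | 0.715 | 0.62-0.65 | 0.64-0.65 |
| Even over 9 months | 75% | 0.625 | 0.50-0.54 | 0.53-0.54 |

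**Step 4: break-even without an entry model.** Suppose no patient is lost. By design effect, 0.80 at the four stated ratios needs mean follow-up of 0.974, 1.011, 0.944 and 0.964 year. Where this is attainable at all, average entry must fall within about three weeks of go-live (1 − 0.944 = 0.056 year). Adding 0.005 to each ratio for rounding gives 0.933, 0.949, 0.927 and 0.938, or about four weeks. The random-intercept form needs more than one year in all four cases.

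**Step 5: detectable ratios at 0.80 (design effect).**

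| Basis | Span at rate 2 | Span at rate 4 |
|---|---|---|
| J.3 | 1.22-1.49 | 1.15-1.33 |
| 12 first visits per year | 1.23-1.50 | 1.16-1.34 |
| 4 first visits per year | 1.25-1.55 | 1.17-1.37 |
| Even entry | 1.31-1.70 | 1.22-1.47 |

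The generous-case ratios stay inside J.3's spans. The conservative ends move outside them.

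**The case against.** The strongest reply has five parts.

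- **The formula is unknown and the match is not exact.** At one person-year both forms miss the two conservative-case ratios by 0.01 to 0.02, and the design-effect form fits slightly better at 0.95 year. This stands as a limit on precision. It does not rescue the plan, because neither 0.625 nor 0.75 year reproduces the set.
- **The mild end is within method slack.** The random-intercept form gives 0.78-0.80 even at full exposure, and at 12 first visits per year it loses only about 2.5 points (0.798 to 0.772 in the first case). This also stands: if nearly everyone enters in the first month, the result could not be told apart from 0.80.
- **The 0.80 is printed only in the Aim 1 sentence.** That is true. But J.3 describes a single power analysis covering both CSSRS and visit rates, and the H2 ratios are approximated at 0.80.
- **The large losses need an entry pattern the documents do not give.** Front-loading is plausible, and at 4 first visits per year the patient count hardly changes. Lost follow-up alone still brings power to about 0.70.
- **J.3 is already a sensitivity range.** It varies ICC, patients per clinic and visit rate, but not follow-up.

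In addition, E.2 limits clinicians' access rather than outcome observation, so the 12-month cap on data rests mainly on section O. Extra-Poisson variation in visits would shrink the loss from shorter follow-up but not reverse it.

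**Conclusion.** The point holds. J.3 and F.3 give different accrual periods, nothing reconciles them, and J.3's H2 ratios assume close to a full year of follow-up for every patient counted over a full year. Under F.3, power at those ratios is below the stated 0.80 under every staggered entry pattern tried. The shortfall ranges from a few points with very early entry to about 30 with even entry. These are illustrations, not bounds: they rest on assumed entry patterns, a 7 v 8 clinic split and two standard formulas standing in for an unstated one. The direction is secure; the size is not, and confidence in it is medium. For H1 only the patients-per-clinic input changes, and no revised H1 figure is claimed. This should be fixed, although the conduct of the trial is not at issue.

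**What to change.** In J.3:

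1. Replace the one-year patient numbers with nine-month numbers.
2. State the expected entry pattern and the mean person-time per patient. The one-year preliminary data may supply both: count patients whose first eligible visit falls in months 1 to 9, and take the mean time from that visit to month 12. J.3 assumes the high-suicide-risk share, so those data may lack suicide scores. If so, the timing of first visits among all patients eligible for the opioid decision support could serve as a declared approximation.
3. Recompute the H2 detectable ratios on that basis.
4. Recompute the H1 detectable percentages by the sponsor's own method with the nine-month patients per clinic. That is about 6, 12 and 25 with even entry (93.75, 187.5 and 375 divided by 15), or about 8, 16 and 32 at 4 first visits per year.

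The cost is a recalculation and restated figures in one section. Enrolment does not change, but the stated detectable effects will be less favourable.

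### The worst-case H1 detectable effect at a 5% control rate is given as 54.8% with RR=5.80, but 54.8%/5% is 10.96, so the risk ratio is understated almost two-fold

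*Combined protocol and SAP*

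**What the plan says.** Section J.3 states its purpose directly: "A power analysis estimated the minimum detectable risk ratio for CSSRS and visit rates in intervention relative to control clinics". For H1 (CSSRS completion) it reports four pairs, each an intervention-arm screening percentage with its risk ratio.

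- Control rate 3%, most favourable scenario: "14.2% (ICCclin=0.01, 33 pts/clin, risk ratio = 4.72").
- Control rate 3%, least favourable scenario: "65.0% (ICCclin=0.05, 8 pts/clin, RR=21.66").
- For "outcomes with a 5% screening rate among control clinic patients", both ends of the range come in one phrase: "is 16.8% (RR=3.36) to 54.8% (RR=5.80").

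The 5% sentence does not repeat the ICC and cluster size. It introduces its range as comparable to the 3% range, so its ends are read here as the same two scenarios (ICC 0.01 with 33 patients per clinic; ICC 0.05 with 8 patients per clinic). Four further pairs are given for the Aim 2 visit rates.

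**The concern.** Once the control rate is fixed, the percentage and the risk ratio are one quantity on two scales, so they must agree. At 5%, the pair 54.8% and 5.80 does not, and the gap is far too large for rounding.

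The detectable risk ratio is the quantity this section sets out to give, and H1 is the Aim 1 hypothesis. A reader who takes the risk ratio at face value would think a 5.8-fold increase is detectable under the most conservative assumptions, when the percentage beside it requires about an 11-fold increase. The error also distorts the comparison between control rates: the worst-case risk ratio appears to fall from 21.66 at 3% to 5.80 at 5%, when it falls only to about 11.

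**Working it through.** **Step 1. Divide each H1 percentage by its control rate (all figures from J.3).**

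| Control rate | Scenario | Stated % | Stated RR | % / control rate |
|---|---|---|---|---|
| 3% | ICC 0.01, 33 per clinic | 14.2% | 4.72 | 4.73 |
| 3% | ICC 0.05, 8 per clinic | 65.0% | 21.66 | 21.67 |
| 5% | ICC 0.01, 33 per clinic | 16.8% | 3.36 | 3.36 |
| 5% | ICC 0.05, 8 per clinic | 54.8% | 5.80 | **10.96** |

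Three pairs agree to rounding. The fourth does not: 54.8/5 = 10.96, and in reverse 5.80 × 5% = 29.0%. The ratio is 10.96/5.80 = 1.89.

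**Step 2. Decide which of the two numbers is wrong.** Division alone cannot say. J.3 names no power method, so a formula has to be reconstructed and tested against the other stated figures. Section J.1 plans Poisson-type mixed models for both outcomes, so a Poisson-regression sample-size formula for a binary exposure is a natural candidate:

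N = DE × [1.960 × √4 + 0.842 × √(2 + 2/RR)]² / [p × (ln RR)²], with DE = 1 + (m − 1) × ICC.

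Inputs:
- power 0.80 and alpha 0.05, read as two-sided (J.3);
- equal arms, an approximation to 1:1 allocation of 15 clinics (E.2);
- p = control screening rate, or visits per year for Aim 2 (J.3);
- N = 500 with m = 33 and ICC 0.01, so DE = 1 + 32 × 0.01 = 1.32;
- N = 125 with m = 8 and ICC 0.05, so DE = 1 + 7 × 0.05 = 1.35.

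Solving for RR:

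| Outcome, control rate | Scenario | Stated RR | Formula RR |
|---|---|---|---|
| CSSRS, 3% | best | 4.72 | 4.72 |
| CSSRS, 3% | worst | 21.66 | 21.81 |
| CSSRS, 5% | best | 3.36 | 3.36 |
| Visits, 2/year | best | 1.22 | 1.22 |
| Visits, 4/year | best | 1.15 | 1.15 |
| Visits, 2/year | worst | 1.49 | 1.49 |
| Visits, 4/year | worst | 1.33 | 1.33 |
| **CSSRS, 5%** | **worst** | **5.80** | **11.02 (55.1%)** |

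Six of the other seven figures match to two decimals and the seventh is within 1%. The disputed cell comes out next to 54.8% and nowhere near 5.80.

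**Step 3. Ask what sample size each candidate RR would need** (p = 0.05, DE = 1.35).

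- RR 10.96: ln RR = 2.394, (ln RR)² = 5.732, squared bracket = 26.66. N = 1.35 × 26.66/(0.05 × 5.732) = 125.6, against 125 in the scenario.
- RR 5.80: ln RR = 1.758, (ln RR)² = 3.090, squared bracket = 27.13. N = 1.35 × 27.13/(0.05 × 3.090) = 237, almost twice the 125 available.

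**Step 4. A check that needs no full formula.** If the variance of the log risk ratio is proportional to 1/p, the detectable ln RR scales with 1/√p. Carrying the stated 3% worst case to 5% gives exp[ln 21.66 × √(0.03/0.05)] = 10.83, or 54.1%. The same scaling of the best case gives 3.33 (16.6%; stated 3.36, 16.8%).

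**Step 5. Could another method give 5.80?** Some two-proportion and log-odds formulas do give risk ratios of 5 to 7 for this cell. But they give only about 7 to 12 where the protocol states 21.66, so they cannot be what was used.

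**The case against.** The best case on the other side is that this is a slip in one parenthetical value. J.3 expresses detectability first as the percentage of intervention patients who must be screened, and that percentage, 54.8%, appears right. The protocol never states 29%; a reader reaches it only by ignoring the printed figure. The 3% worst case next to it (65.0%, RR 21.66) already shows openly how weak power is with few patients per clinic. The number of clinics is fixed at 15 by the parent trial, so no sample size was derived from 5.80. A benign origin is plausible: the same Poisson formula gives 5.89 for a neighbouring scenario in the protocol's own grid (16 patients per clinic, ICC 0.03, 5% control), so a value may have come from another row, although the figures do not match and only the source output can settle it.

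Most of this stands as a limit on consequence. Correcting the figure changes no hypothesis, model or accrual target. It is also fair that the formula above is a reconstruction, since the protocol states no method. What does not follow is that the point can be left: the two numbers cannot both be right, and the wrong one is the effect measure the section says it is estimating.

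**Conclusion.** The concern holds. At a 5% control rate, 54.8% and RR=5.80 are incompatible, and the evidence identifies 5.80 as the error. The worst-case detectable risk ratio for H1 should be about 10.96 (reconstruction: 11.02), so it is understated by a factor of 1.89.

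The inconsistency rests on division alone. Attributing it to the risk ratio rather than the percentage rests on three assumptions: the 5% range uses the same two scenarios as the 3% range, the test is two-sided, and the method behaves like the Poisson formula that reproduces the other seven figures. This is a wrong power figure for a primary hypothesis and should be corrected. It does not show that the rest of the power analysis is faulty.

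**What to change.** Retrieve the power output for ICC 0.05, 8 patients per clinic and a 5% control rate. If it confirms 54.8%, replace RR=5.80 with RR=10.96 in section J.3. If it shows something else, restate both figures from that one scenario so that the percentage divided by 5% equals the risk ratio. It would help to repeat the ICC and cluster size in the 5% sentence, as the 3% sentence does, and to name the formula or software.

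The cost is one number and a short clarification. The stated worst-case risk ratio becomes less favourable; the design and analysis stay as they are.
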